3.1.3 End of Study

The end of study is defined as the first day when all patients have had a study completion visit or early termination visit or have otherwise been discontinued from the study.

3.2 RATIONALE FOR STUDY DESIGN

3.2.1 Rationale for Study Design

Hospitalized influenza A infection represents a high unmet need, which, when left untreated, may progress to a more serious disease that may result in significant morbidity and mortality in otherwise healthy adults as well as in vulnerable populations.

This study is designed to estimate the improvement in outcome of a combination regimen of MHAA4549A with oseltamivir compared to a standard of care arm of placebo with oseltamivir. The study population will include hospitalized patients with influenza A requiring *ongoing* O₂ support and/or PPV support within 24 hours of hospital admission.

Study GV29216 will be a Phase 2b study involving approximately 330 patients. The sample size was determined based on an expected clinically meaningful difference of 1–2 days improvement in time to normalization of respiratory function between the control and treatment arms, assuming a 5 day median time to the time to normalization of respiratory function in the standard of care arm ([Blackwood et al. 2011](#); [Premier Inc, Charlotte, NC](#)).

This design ensures that all patients in the trial will receive the current NAI treatment, oseltamivir, as standard of care at a minimum, and will evaluate the clinical benefit of combining MHAA4549A with this standard of care regimen. Therefore, this study aims to identify a regimen that could deliver maximum benefit in this high unmet need disease, while still treating all enrolled patients with the currently accepted standard of care.

3.2.2 Rationale for Patient Population and Primary Endpoint

Severe influenza, for the purpose of this study, is defined as requiring one of the following treatments: any supplemental O₂ to maintain an SpO₂ > 92% or PPV. PPV is

defined as any mechanical positive pressure device to maintain oxygenation; this can include positive pressure mask and intubation.

This patient population was chosen based on the rationale that respiratory failure is a hallmark of influenza and a major driver of morbidity and mortality, as well as hospitalization. The recovery from ventilator support has been shown to be directly proportional to time spent in the ICU (Blackwood et al. 2011; Premier Inc, Charlotte, NC). Based upon an analysis of morbidity and mortality, the patient population that requires supplemental O₂ or ventilation on their first day of admission was determined to have a high unmet medical need as they have an estimated mortality of 9%-32%, and 27% require admission to the ICU, according to analysis of a database of over 70,000 hospitalized patients in the U.S. from 2005-2012 (Premier Inc, Charlotte, NC).

The proposed primary efficacy outcome measure in this study is “Time to normalization of respiratory function,” defined as oxygen saturation \geq 95% without oxygen supplementation. Support for use of a respiratory endpoint in this population comes from recently published data demonstrating that a composite endpoint that captured respiratory rate, fever, heart rate, and blood pressure resolution was primarily driven by the respiratory component of the endpoint (Marty et al. 2014). Given that influenza infections generally do not cause systemic infections and influenza disease is restricted to the respiratory tract, the Sponsor believes that the primary endpoint represents a clinically meaningful outcome in this patient population (as shown by analysis of PREMIER database) and measures an important physiologically relevant pharmacodynamic response parameter of MHAA4549A. This endpoint is a measure of patient function, measures a symptom that represents a serious consequence of influenza, and is consistent with clinically relevant endpoints discussed in the US Food and Drug Administration (FDA) Guidance, “Influenza: Developing Drugs for Treatment and/or Prophylaxis” (FDA 2011).

3.2.3 Rationale for Control Group and Treatment Window

In this study, the standard of care regimen for the control or comparator group (*hospitalized influenza A patients*) is oseltamivir, an NAI. In the treatment groups, MHAA4549A will be dosed in addition to oseltamivir. *Oseltamivir* for a minimum of 5 days is permitted following treatment with MHAA4549A. Treatment for longer than 5 days is permitted based on local investigator discretion (WHO 2005; Fiore et al. 2011; CDC 2016). The oseltamivir dosing regimen is listed in Table 2. This control treatment was based on consideration of safety, ethics, and efficacy for treatment of severe influenza and is consistent with guidelines for antiviral treatment of hospitalized patients with influenza (Harper et al. 2009; Fiore et al. 2011).

Table 2 Oseltamivir Dosing Regimen

Neuraminidase Inhibitor	Dosing Regimen	Duration of Therapy
Oseltamivir	75 mg or 150 mg oral twice daily ^a	5 days ^b

^a 75 mg or 150 mg dose at the discretion of the investigator, and dose must be documented. Capsules can be opened and the granules administered via nasogastric tube, if required. For renal dose adjustments, follow local standard of care practice/local package insert and document in the eCRF.

^b Longer treatment times are at the discretion of the investigator (WHO 2005; Fiore et al. 2011; CDC 2016).

If oseltamivir resistance is highly suspected or identified or oseltamivir route of administration challenges are encountered, then following discussion with the Sponsor Medical Monitor, an alternative NAI to oseltamivir may be used. *For renal dose adjustments, local standard-of-care practice/local package insert should be followed and documented in the eCRF. Capsules other than 75 mg (for 75 mg twice a day [BID] or 150 mg BID regimens) cannot be provided through the study Interactive Voice and Web Response System (IxRS). In these instances, the study site may supply the appropriate dose and be reimbursed by the Sponsor.*

From a safety standpoint there are no expected drug interactions between MHAA4549A, a monoclonal antibody, and any NAI, which are small molecule drugs that bind to a different viral protein than MHAA4549A. In the Phase 2a challenge study, all subjects that were dosed with MHAA4549A also received a 5-day course of oseltamivir starting on Day 7. There were no safety effects attributable to the combination when the drugs were present concurrently. *In the Phase 2a challenge study, MHAA4549A treatment did not appear to impact the exposure of oseltamivir and its active metabolite oseltamivir carboxylate. There was no suggestion of PK drug-drug interaction between MHAA4549A and oseltamivir.*

For this Phase 2b study, a combination of MHAA4549A and oseltamivir was determined to be the most clinically feasible treatment regimen, both from an ethical as well as a practical perspective. The treatment of all patients with oseltamivir ensures that all patients will receive the standard of care. Given the high morbidity and mortality of hospitalized patients with influenza A along with guidelines from Centers for Disease Control and Prevention (CDC) and Infectious Diseases Society of America (IDSA) it is recommended that NAIs are the standard of care for hospitalized patients with influenza A (Harper et al. 2009; CDC 2016). Furthermore, pre-clinical efficacy data from a study using MHAA4549A and oseltamivir in combination showed a potential synergistic effect of both compounds which may be due to the different and potentially complementary mechanisms of action, i.e. targeting viral HA and neuraminidase (NA).

Dosing of MHAA4549A is confined to a treatment window designed for best expected treatment success and to ensure that any observed effects can be attributed to the study

drug with high confidence. MHAA4549A shall only be dosed within 5 days of onset of symptoms (including fever, chills, malaise, dry cough, loss of appetite, myalgias, coryza, or nausea), no later than 48 hours after admission to the hospital, and if a subject has taken less than a total of 6 doses (3 doses for peramivir) of approved anti-influenza therapy from onset of symptoms. This proposed window is supported by data demonstrating that hospitalized influenza patients benefit from NAI treatment even at 5 days from onset of symptoms (Louie et al. 2012). The patient must start standard-of-care oseltamivir no later than 12 hours after completion of MHAA4549A administration.

3.2.4 Rationale for MHAA4549A Dosage

[figure not shown]
Single IV doses of 3600 and 8400 mg were selected to assess the safety, efficacy, and pharmacokinetics of MHAA4549A and to provide data for further clinical development. The selection of dose in this study was based on nonclinical efficacy data from the in vivo mouse influenza A infection models, the pharmacokinetics in clinical studies, and the relationship between the pharmacokinetics, pharmacodynamics, and efficacy observed in the Phase 2a challenge study in influenza A (GV28985).

The dose of 3600 mg is based on the Phase 2a challenge study (GV28985), which demonstrated both a significant decrease in viral shedding in the upper respiratory tract and a decrease in the AUC of symptoms scores in patients who received the 3600-mg dose of MHAA4549A as compared to patients who received placebo (see Section 1.2.4). An exploratory exposure-response analysis of this group demonstrated that subjects with nasal viral loads greater than the median viral load had shorter time to resolution of viral shedding as compared with the placebo group (median: 75.8 hours vs. 113.7 hours), whereas subjects with nasal viral loads less than the median viral load had similar time to resolution of viral shedding compared with the placebo group (median: 112.1 hours vs. 113.7 hours). Thus, at higher viral loads, higher doses of MHAA4549A are expected to be more efficacious.

The 8400-mg dose was selected based on the hypothesis that severely ill patients hospitalized with influenza infection (the target population of MHAA4549A) are likely to have high viral loads and longer durations of viral shedding and require increased doses of MHAA4549A. Simulations from a semi-quantitative pharmacokinetic model developed from the Phase 2a challenge study (GV28985) suggest that 8400 mg is the minimum dose that will show a separation of nasal exposure from a dose of 3600 mg (Figure 2).

Both the 3600- and 8400-mg doses of MHAA4549A are expected to be safe based on previous clinical Phase 1 Phase 2a studies.

Figure 2 Semi-Quantitative Pharmacokinetic Model of Nasal Exposure

Note: The bottom and top of the box represent the 25th and 75th percentile, and the band inside the box is the median ($n = 100$ per dose level). The upper whisker is the 1.5 interquartile range (IQR) of 75th percentile and the lower whisker is the 1.5 IQR of 25th percentile. Single dots represent outliers. Simulation assumes PK can be extrapolated at doses above 3600 mg and that the PK profile in acute uncomplicated influenza A infection is similar to the PK profile of severely ill patients.

3.2.5 Rationale for Biomarker Assessments

[Redacted text block]

[Redacted text block]

[Redacted text block]

[REDACTED]

[REDACTED]

3.3 OUTCOME MEASURES

3.3.1 Safety Outcome Measures

The safety outcome measures for this study are as follows:

- AEs and clinical laboratory abnormalities
- Vital signs, physical findings, ATAs, and clinical laboratory results during and following administration of MHAA4549A

3.3.2 Primary Efficacy Outcome Measures

The primary efficacy outcome measure for this study *is* as follows:

- Time to normalization of respiratory function defined as:
 - The time to cessation of O₂ support resulting in a stable SpO₂ ≥ 95% (see [Appendix 2](#) for details)

3.3.3 Secondary Efficacy Outcome Measures

The secondary efficacy outcome measures for this study are as follows:

- *Clinical status of patient at Days 1–7, 14, and 30. This is an ordinal outcome with six mutually exclusive categories:*
 1. *Death;*
 2. *In the ICU;*
 3. *Non-ICU hospitalization, requiring supplemental oxygen;*
 4. *Non-ICU hospitalization, not requiring supplemental oxygen;*
 5. *Not hospitalized, but unable to resume normal activities; or*
 6. *Not hospitalized with full resumption of normal activities*
- Clinical failure after 24 hours post-infusion of study drug; defined as:
 - Progression to increased O₂ requirement defined by an increase in oxygen supplementation from low flow oxygen (i.e., 2–6 L/min) to high flow oxygen

(i.e., >6 L/min) or from oxygen supplementation alone to any PPV or extracorporeal membrane oxygenation (ECMO)

- Progression to ICU
- Prolonged ventilation or O₂ support defined by >2 weeks, or
- Death
- Time to clinical resolution of *abnormal* vital signs (3/5 criteria must be met):
 - SpO₂ ≥ 95% without supplemental O₂
 - Respiratory rate < 24 breaths per minute without supplemental O₂
 - Core temperature < 37.2°C immediately prior to receipt of any antipyretic drug, and at least 6-8 hours from the last dose of antipyretic or core temperature > 36°C in patients who are initially hypothermic
 - Heart rate (HR) < 100 beats/minute
 - Systolic blood pressure (SBP) > 90 mmHg
- All-cause mortality at Day 14, Day 30, and Day 60
- Influenza A viral load in nasopharyngeal samples
 - AUEC (qPCR)
 - Peak viral load (qPCR)
 - *Duration of viral shedding* (qPCR)
- Duration of hospitalization
- Duration of ICU stay
- Antibiotic usage for respiratory infections
- Complications of influenza:
 - Pneumonia (HAP/VAP)
 - Exacerbations of chronic lung disease
 - Myocarditis
 - ARDS
 - Otitis media
 - Other related complications
- All-cause readmission at Day 30 and Day 60
- Duration of ventilation

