 4. *Non-ICU hospitalization, not requiring supplemental oxygen;*
 5. *Not hospitalized, but unable to resume normal activities; or*
 6. *Not hospitalized with full resumption of normal activities*
- Clinical failure after 24 hours post-infusion of study drug defined as:
 - Progression to increased O₂ requirement defined by an increase in oxygen supplementation from low flow oxygen (*i.e.*, 2 – 6 L/min) to high flow oxygen (*i.e.*, > 6 L/min) or from oxygen supplementation alone to any PPV or ECMO
 - Progression to ICU
 - Prolonged ventilation or O₂ support defined by >2 weeks, or
 - Death

- Time to clinical resolution of *abnormal* vital signs (3/5 criteria must be met):
 - SpO₂ ≥ 95% without supplemental O₂
 - Respiratory rate < 24 breaths per minute without supplemental O₂
 - Core temperature < 37.2°C immediately prior to receipt of any antipyretic drug, and at least 6-8 hours from the last dose of antipyretic or core temperature > 36°C in patients who are initially hypothermic
 - Heart rate (HR) < 100 beats/minute
 - Systolic blood pressure (SBP) > 90 mmHg
- All-cause mortality at Day 14, Day 30, and Day 60
- Influenza A viral load in nasopharyngeal samples
 - Area under viral load-time curve (AUEC; qPCR)
 - Peak viral load (qPCR)
 - *Duration of viral shedding* (qPCR)
- Duration of hospitalization
- Duration of ICU stay
- Antibiotic usage for respiratory infections
- Complications of influenza:
 - Pneumonia (HAP/VAP)
 - Exacerbations of chronic lung disease
 - Myocarditis
 - ARDS
 - Otitis media
 - Other related complications
- All-cause readmission at Day 30 and Day 60
- Duration of ventilation

Pharmacokinetic Outcome

The primary PK outcome measures for this study are as follows:

- PK parameters for MHAA4549A in serum including total exposure (i.e., area under the curve [AUC]), maximum observed concentration (C_{max}), clearance, half-life, and volume of distribution, when appropriate, as data allow

The exploratory PK outcome measures for this study are as follows:

- [REDACTED]
- [REDACTED]

Exploratory Outcome Measures

The exploratory outcome measures for this study are as follows:

- [REDACTED]
- [REDACTED]
- [REDACTED]
- [REDACTED]
- [REDACTED]

[REDACTED]

Investigational Medicinal Products

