4.5.1 Permitted Therapy

Patients who use oral contraceptives, hormone-replacement therapy, or other maintenance therapy should continue their use.

All therapies required for management of the patient's acute illness are permitted except for those listed below in [Section 4.5.2](#).

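### In initially hypothermic patients the temperature component of vital-sign resolution is met at essentially any temperature, so it cannot discriminate

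*Combined protocol and SAP*

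**What the plan says.** Section 3.3.3 of the protocol (Version 7) lists time to clinical resolution of abnormal vital signs among the secondary efficacy outcomes, with the rule "3/5 criteria must be met". The temperature component has two limbs:

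- First limb, for any patient: "Core temperature < 37.2°C immediately prior to receipt of any antipyretic drug, and at least 6-8 hours from the last dose of antipyretic".
- Second limb: "or core temperature > 36°C in patients who are initially hypothermic".

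The Synopsis repeats the second limb, "core temperature > 36°C in patients who are initially hypothermic", also without an upper limit. No threshold for being initially hypothermic appears in the text available.

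The other components are "SpO₂ ≥ 95% without supplemental O₂", "Respiratory rate < 24 breaths per minute without supplemental O₂", heart rate below 100 beats per minute, and "Systolic blood pressure (SBP) > 90 mmHg". Section 6.4.2 names the summary for this endpoint (a median time), and Section 6.4 gives the general time-to-event method. Neither adds a temperature bound.

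**The concern.** The second limb is evidently there so that a cold patient is not called resolved until warm. As written it does not do this. Because the limbs are alternatives, a patient who started cold can meet the component by overshooting into fever, or through the first limb without warming at all.

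Appendix 8 of the protocol grades 39.0–40.0°C as severe (Grade 3) fever, so a reading that the plan elsewhere grades as severe would be scored here as temperature resolved. In this subgroup one of the five components is close to automatic, and only two more are then needed. The endpoint would tend to record resolution too early in these patients.

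**Working it through.** The plan gives no figure to reproduce; the check is of the rule's logic.

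**Coverage of the two limbs.** Let T be core temperature. For an initially hypothermic patient the component is met if T < 37.2 or T > 36. Any T that fails the first limb is at least 37.2, hence above 36, and so meets the second. The union is every temperature. The antipyretic condition is attached only to the first limb. The one region left uncovered is therefore T ≤ 36 within the antipyretic interval.

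Applying the rule as written, with the antipyretic condition taken as satisfied, and then with both limits required (36 < T < 37.2):

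| T (°C) | Initially hypothermic, as written | Other patients, as written | Initially hypothermic, both limits |
|---|---|---|---|
| 34, 35, 35.9, 36 | met | met | not met |
| 36.1, 37.1 | met | met | met |
| 37.2, 38, 39, 40.5 | met | not met | not met |

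As written, the initially hypothermic patient passes at all ten values. With both limits required, the patient passes at two.

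**What one automatic component does to the three-of-five rule.** The five components give 2⁵ = 32 met/not-met patterns. Those with at least three met number C(5,3) + C(5,4) + C(5,5) = 10 + 5 + 1 = 16.

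- Temperature met: at least two of the other four are needed, C(4,2) + C(4,3) + C(4,4) = 6 + 4 + 1 = 11 of 16 patterns.
- Temperature not met: at least three of the other four are needed, C(4,3) + C(4,4) = 4 + 1 = 5 of 16 patterns.

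These are counts of patterns, not probabilities. One resolving pattern is temperature, heart rate and blood pressure met with both respiratory components failed. An initially hypothermic patient now at 39°C, with heart rate below 100 and systolic pressure above 90, would be an event while still on oxygen.

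**Whether another section repairs it.** Appendix 1a asks for the most abnormal value of the day when several are taken. That does not help, since 39.5°C and 35°C both pass. Section 4.6.8 governs how temperature is measured, not how it is scored.

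**Size of the subgroup.** The documents do not give it. If, purely as an assumption, 2–5% of patients were initially hypothermic, that would be 0.02 × 330 = 6.6 to 0.05 × 330 = 16.5 of the 330 enrolled. The efficacy set is restricted to centrally PCR-confirmed patients, so the number analysed could be lower. These are patients to whom the defect applies, not patients misclassified.

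**The case against.** The best reply is that the outcome's name refers to abnormal vital signs. Read for its purpose, the 36°C limb describes recovery from hypothermia, and no sensible programmer would score a new fever as resolution. Section 6 also leaves further analysis detail to a separate SAP, and only part of the combined document is available, so a derivation rule may exist. Both points are fair, but they do not remove the problem. The written rule gives the wrong answer when followed, and nothing in the available text corrects it.

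It is also said, rightly, that the consequence is small: a secondary outcome in an estimation study with no formal testing, randomized and blinded, so misclassification would more plausibly dilute a difference than favour an arm.

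Three stronger readings are tempting and are not supported.

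- A reader might infer that a febrile patient is thereby resolved. Only one component is met; two more are required.
- A reader might infer that the blood pressure component is wrong because it counts pressure held up by vasopressors. The plan is silent on this. Such drugs are permitted, since "All therapies required for management of the patient's acute illness are permitted except for those listed below" and they are not on the prohibited list. The two respiratory components do require the patient to be off oxygen, so the contrast is worth noting. But no passage says that supported pressure should not count, and nothing is contradicted.
- A reader might want a number of patients with drug-supported pressure. The documents give no rate of vasopressor use. The ICU share quoted in Section 3.2.2 comes from a US hospital database, not from this trial, and some treated patients would exceed 90 mmHg unaided.

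**Conclusion.** The point holds for the temperature component. In initially hypothermic patients the two limbs together admit every temperature, antipyretic timing aside, so both new fever and persisting hypothermia count as meeting it. This follows from the wording alone and needs no assumption about rates.

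The effect is confined to one of five components of one secondary endpoint, in a subgroup of unstated size. Its influence on the median or the hazard ratio cannot be calculated from the documents. The primary endpoint and the planned 330 patients are untouched. The conclusion assumes that no rule outside the available text already bounds the component.

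The blood pressure component is a matter for an optional sensitivity analysis and is not an error.

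**What to change.** In Section 3.3.3 and the Synopsis, restate the temperature component as core temperature below 37.2°C under the antipyretic condition already stated and, in patients initially hypothermic, also above 36°C. Both limits are the plan's own. In the same sentence, state the threshold that makes a patient initially hypothermic and the reading it is taken from; Section 6.3 already defines baseline as the last value before study drug. Carry the same rule into the SAP before it is finalised, which Section 6 places ahead of the first interim or final analysis.

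The cost is one phrase in two places. No new measurement is needed, and some resolution times in this subgroup will become later.

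Optionally, add a sensitivity analysis that does not count systolic pressure above 90 mmHg as met on days with recorded vasopressor use. Section 4.5 has concomitant medications recorded throughout, but the text does not show that dates are precise enough to align with vital-sign readings, so feasibility should be checked first.
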